6.2.1 Clinic Visit 15 (OLE Study Day 1)

Part 2 Visit 15 will occur 14 days (± 4 days) after Part 1 Visit 12. The 14-day transition period preceding Visit 15 may be extended up to 14 days in the case of a required safety adjudication of a Visit 12 ECHO alert.

The following procedures will be performed during Visit 15:

- Ensure entry criteria for Part 2 are met
- Vital signs
- Record prior and concomitant medications (use core study Visit 12 information)
- Instruct parent/caregiver on use of diary
- Record ongoing AEs as medical history
- Record ongoing AESI as medical history
- Collect, review, and dispense diary (after above procedures have been concluded)
- Dispense study medication

Data collected from Part 1 Visit 12 may be used for the following procedures unless otherwise indicated:

- Record medical, neurological, and epilepsy history
- Complete physical examination, including height and weight (use data collected at Part 1 Visit 12, unless there was a significant change in subject status warranting a new complete examination)
- Complete neurological examination (use data collected at Part 1 Visit 12, unless there was a significant change in subject status warranting a new complete examination)

ZX008 (Fenfluramine Hydrochloride)
ZX008-1601 Clinical Study PA 4.0 (Japan) 25 July 2022

- 12-lead ECG
- Doppler ECHO
- Laboratory evaluation (serum chemistry, hematology, immunoglobulin, hormones, and urinalysis) (use Part 1 Visit 12 information, unless investigator determines new laboratory evaluation is warranted due to change in subject status) (if collecting urine for urinalysis, urine may be collected at home, the night before the clinic visit, as long as collection procedures are followed to maintain sample stability)
- Pregnancy test
- Urine or serum THC panel
- Whole blood CBD
- C-SSRS Since Last Visit Assessment ([Appendix 2](#))
- CGI-I (assessed by parent/caregiver)
- CGI-I (assessed by investigator)
- BRIEF ([Appendix 3](#))
- QOLCE ([Appendix 6](#))
- HADS ([Appendix 7](#))
- Zarit Caregiver Burden Inventory ([Appendix 8](#))

6.2.2 Clinic/Phone Visit 16 (OLE Study Day 15)

Part 2 Visit 16 may be performed in the clinic, or, at the discretion of the investigator, performed via phone.

If Visit 16 is performed in the clinic, subjects will report to the clinic in the morning of that day. The following procedures will be performed:

- Review current seizure activity (number/type/duration) from diary since previous visit
- Record concomitant medications since previous visit
- Obtain weight
- Vital signs
- Laboratory evaluation (serum chemistry, hematology, immunoglobulin, hormones, and urinalysis) (only if investigator determines new laboratory evaluation is warranted due to change in subject status since Visit 15) (if collecting urine for urinalysis, urine may be collected at home, the night before the clinic visit, as long as collection procedures are followed to maintain sample stability)
- Collect, review, and dispense diary. Ensure diary is being completed daily; if diary compliance is low (i.e. <90%), re-train parent/caregiver.
- Record AEs
 - Perform an abbreviated physical and/or neurological examination as appropriate based on last exam and reported AEs
 - Collect plasma sample for AED pharmacokinetic evaluation if clinically indicated (must document time of last dose)
- Record AESI
- Collect used, partially used and unused study medication; perform drug accountability and review with parent/caregiver

ZX008 (Fenfluramine Hydrochloride)
ZX008-1601 Clinical Study PA 4.0 (Japan) 25 July 2022

- Collect and review study medication

If the visit is performed as a phone visit, site personnel will contact the subject on Study Day 15 and record/review the following:

- Concomitant medications
- AEs
- AESI
- Study medication use
- Diary entries

6.2.3 Clinic Visits 17-21 (OLE Months, 1, 2, 3, 6, and 9)

Subjects will report to the clinic for Part 2 Clinic Visits 17 through 21. The following procedures will be performed:

- Review current seizure activity (number/type/duration) from diary since previous visit
- Record concomitant medications
- Obtain weight (**Note: if the subject's weight is $\pm 25\%$ of the weight at Part 2 Day 15, the IMP dose will be recalculated**)
- Obtain vital signs
- 12-lead ECG
- Doppler ECHO (at Months 1, 3, 6, and 9)
- Urine or serum pregnancy test for females of child-bearing potential (at Months 3, 6, and 9)
- Laboratory evaluation (serum chemistry, hematology, immunoglobulin, hormones, and urinalysis; at Months 3, 6 and 9 unless otherwise clinically indicated) (urine for urinalysis may be collected at home, the night before the clinic visit, as long as collection procedures are followed to maintain sample stability)
- Urine or serum THC panel (at Months 3, 6 and 9)
- Whole blood CBD (at Months 3, 6, and 9)
- Collect plasma sample for AED PK and document time of last dose (at Months 3, 6, and 9 unless otherwise clinically indicated)
- Tanner Staging for subjects > 7 to 18 years of age (Month 6 only) ([Appendix 5](#))
- Collect, review, and dispense diary. Ensure diary is being completed daily; if diary compliance is low (i.e. <90%), re-train parent/caregiver.
- C-SSRS Since Last Visit Assessment ([Appendix 2](#))
- CGI-I (assessed by parent/caregiver)
- CGI-I (assessed by investigator)
- BRIEF (Month 6 only) ([Appendix 3](#))
- QOLCE (Month 6 only) ([Appendix 6](#))
- HADS (Month 6 only) ([Appendix 7](#))
- Record AEs
 - Perform an abbreviated physical and/or neurological examination as appropriate based on last exam and reported AEs

ZX008 (Fenfluramine Hydrochloride)
ZX008-1601 Clinical Study PA 4.0 (Japan) 25 July 2022

- Collect plasma sample for AED pharmacokinetic evaluation if clinically indicated
- Record AESI
- Collect used, partially used and unused study medication; perform drug accountability and review with parent/caregiver
- Dispense study medication

The next study visit should be Visit 30 (EOS), unless a 1-year extension is granted. If extending study participation, the decision should be made during Visit 21 (or at least prior to conducting Visit 22 procedures) by the Investigator and the consent from the subject or parent/caregiver obtained. After approval from Investigator and Sponsor for extension, Subject will return every 3 months for the 1 year extension (i.e. Month 12, 15, 18, 21). The End of Study will be Visit 30, on the 24th month of OLE, unless another 1 year extension is granted, in which case the subject will continue to return for clinic visits every 3 months (i.e. Month 24, 27, 30, 33) until the EOS Visit 30 on the 36th month of OLE.

6.2.4 Clinic Visit 22 (OLE Month 12)

Subjects will report to the clinic and the following procedures will be performed:

- Review current seizure activity (number/type/duration) from diary since previous visit
- Record concomitant medications
- Obtain weight (**Note: if the subject's weight is $\pm 25\%$ of the weight at Part 2 Day 15, the IMP dose will be recalculated**)
- Complete physical examination, including height and weight, and calculation of BMI
- Complete neurological examination
- Obtain vital signs
- 12-lead ECG
- Doppler ECHO (must be performed any time between Study Day 344 and Study Day 365).
- Urine or serum pregnancy test for females of child-bearing potential
- Laboratory evaluation (serum chemistry and hematology, and urinalysis)
- Urine or serum THC panel
- Whole blood CBD
- Collect plasma sample for AED PK evaluation (must document time of last dose)
- Tanner Staging for subjects > 7 to 18 years of age ([Appendix 5](#))
- Collect and review diary
- C-SSRS Since Last Visit Assessment ([Appendix 2](#))
- CGI-I (assessed by parent/caregiver)
- CGI-I (assessed by investigator)
- BRIEF ([Appendix 3](#))
- QOLCE ([Appendix 6](#))
- HADS ([Appendix 7](#))
- Zarit Caregiver Burden Inventory ([Appendix 8](#))

ZX008 (Fenfluramine Hydrochloride)
ZX008-1601 Clinical Study PA 4.0 (Japan) 25 July 2022

- Record AEs
- Record AESI
- Collect used, partially used and unused study medication; perform drug accountability and review with parent/caregiver
- Dispense study medication

6.2.5 Clinic Visits 23-41 (OLE Months 15, 18, 21, 24, 27, 30, 33, 36, 39, 42, 45, 48, 51, 54, 57, 60, 63, 66, 69)

If marketing approval is not yet received after the the end of the OLE Treatment Period, treatment may be extended on an annual basis in order to provide continuity of treatment for subjects who are enrolled in Part 2 of the study. Continuation will be based on review of safety/tolerability and effectiveness, and be offered for subjects who continue to meet eligibility requirements, comply with investigator's instructions, and for whom the investigator judges benefit outweighs risk.

From Visit 26/Month 24 (or a later visit if Visit 26/Month 24 has already occurred at the time of Protocol Amendment 4.0 approval), if approved for the extensions, subjects will report to the clinic every 6 months and will have a phone visit 3 months after each in-clinic visit for Part 2 Clinic Visits 26 through 41.

The following procedures will be performed during in-clinic visits:

- Record concomitant medications
- Obtain weight (**Note: if the subject's weight is $\pm 25\%$ of the weight at Part 2 Day 15, the IMP dose will be recalculated**)
- Obtain vital signs
- Abbreviated physical examination, as appropriate based on last exam and reported AEs
- Abbreviated neurological examination, as appropriate based on last exam and reported AEs
- 12-lead ECG, if clinically indicated
- Doppler ECHO
- Urine or serum pregnancy test for females of child-bearing potential
- Only if clinically indicated:
 - Laboratory evaluation (serum chemistry, hematology, immunoglobulin, hormones, and urinalysis) (urine for urinalysis may be collected at home, the night before the clinic visit, as long as collection procedures are followed to maintain sample stability)
 - Collect plasma sample for AED PK and document time of last dose
- Seizure Assessment by Investigator
- C-SSRS Since Last Visit Assessment ([Appendix 2](#))
- CGI-I (assessed by parent/caregiver)
- CGI-I (assessed by investigator)
- Record AEs
- Record AESI

ZX008 (Fenfluramine Hydrochloride)
ZX008-1601 Clinical Study PA 4.0 (Japan) 25 July 2022

- Collect used, partially used and unused study medication; perform drug accountability and review with parent/caregiver
- Dispense study medication

The following procedures will be performed during phone visits:

- Record concomitant medications
- Record AEs
- Record AESI

The next study visit after Visit 25/Month 21, Visit 29/Month 33, Visit 33/Month 45, Visit 37/Month 57 or Visit 41/Month 69 should be Visit 42 (EOS), unless another 1-year extension is granted. If extending study participation, the decision should be made during the in-clinic visit preceding the annual reconduction by the Investigator and the consent from the subject or parent/caregiver obtained. After approval from Investigator and Sponsor for extension and starting after Visit 26/Month 24 (or a later visit if Visit 26/Month 24 has already occurred at the time of Protocol Amendment 4.0 approval), subject will return to the clinic every 6 months and will have a phone visit 3 months after each in-clinic visit for the 1 year extension. The End of Study will be Visit 42, the 72nd month of the OLE, or until ZX008 is approved in the subject's country of residence and listed on a patient's health plan formulary, whichever occurs first.

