6.1.1.1 Screening, Clinic Visit 1 (Study Day -28)

Screening is the predetermined series of procedures with which each investigator selects an appropriate and representative sample of subjects for enrollment into the study. Select screening data will be documented in the IWR and eCRF.

Written informed parental or guardian consent and assent of minors (if the subject is capable of providing assent) must be obtained before a subject can start any of the screening procedures. The procedure(s) for obtaining written informed consent and assent of minor (if the subject is capable of providing assent) are described in Section 11.2.

The Screening visit will occur on Study Day -28; however, the procedures may be split over 2 consecutive days (eg, Study Day -29 and Study Day -28 or Study Day -28 and Study Day -27). Splitting the visit procedures across 2 nonsequential days requires the approval of the medical monitor. The following procedures will be performed for all subjects before the start of seizure activity observation:

ZX008 (Fenfluramine Hydrochloride)

ZX008-1601 Clinical Study PA 4.0 (Japan) 25 July 2022

- Obtain written informed consent for the study
- Obtain written informed consent from parent/caregiver to collect information about parent/caregiver symptoms and burden via the Zarit Caregiver Burden, and HADS rating
- Review inclusion and exclusion criteria
- Review retrospective seizure diary data
- Record demographic information
- Record medical, neurological, and epilepsy history
- Record current epilepsy status (number/type/duration seizures per month); submit form to Epilepsy Study Consortium
- Collect past 6 months (or available duration) of parent/caregiver seizure diary data if available (screen shots of cell phones are acceptable, as are photocopies of paper diaries or print outs) and place in source file
- Record prior medications
- Complete physical examination, including height and weight
- Complete neurological examination
- 12-lead electrocardiogram
- Doppler ECHO (this may be obtained any time between Study Day -28 and Study Day -15)
- Vital signs
- Urine or serum pregnancy test for females of child-bearing potential
- Laboratory evaluation (serum chemistry, hematology, immunoglobulin, and urinalysis)
- Urine or serum THC panel
- Whole blood CBD
- C-SSRS Baseline/Screening Assessment ([Appendix 2](#))
- Instruct parent/caregiver on use of diary

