| ECHO | No | Yes, 3 months post-treatment | Yes, 3 and 6 months post-treatment | Yes, 3 and 6 months post-treatment, and every 3 months until resolved, or stable and unlikely to change |
| ECG | No | Yes, 3 months post-treatment | Yes, 3 and 6 months post-treatment | Yes, 3 and 6 months post-treatment and every 3 months until resolved, or stable and unlikely to change |
| Physical examination | No | Yes, 3 months post-treatment | Yes, 3 months post-treatment only | Yes, 3 and 6 months post-treatment, and every 3 months until resolved, or stable and unlikely to change |
| ^a If blind is broken at the end of the study and a subject revealed to have taken only placebo, no further testing is required. ^b Positive sign or symptom includes any development of valve thickening or regurgitation ("trace" or greater in mitral, aortic; mild or greater in pulmonary, tricuspid), or sign or symptom indicative of potential pulmonary hypertension as adjudicated by the ICAB. | | | | |

6.2 Part 2

Review of inclusion and exclusion criteria and written informed parental or guardian consent and assent of minors (if the subject is capable of providing assent) for Part 2 must be obtained before a subject can start any of the Part 2 Visit 15 procedures. This includes review and approval (or adjudication if required) of the ECG and/or ECHO findings by the central reader, and approval for continuation in the open-label extension (if applicable) by the IDSMC.

Only eligible subjects as specified by the inclusion and exclusion criteria who have successfully completed Part 1, or have permission from the Sponsor, will be enrolled into Part 2. Other circumstances for participation in Part 2 are described in Section 4.3.

Study procedures for the Part 2 OLE Treatment Period will be conducted according to the Schedule of Assessments in Table 2. Time windows for all assessments are detailed in Table 11.

ZX008 (Fenfluramine Hydrochloride)**ZX008-1601 Clinical Study PA 4.0 (Japan) 25 July 2022****Table 11: Time Windows for Assessments in Part 2**

| Visit / Procedure | Time window (relative to scheduled visit / procedure) |
|---|---|
| Visit 15 (Clinic; OLE Study Day 1) | ± 4 days ^a |
| Visits 16 (Clinic/Phone; OLE Study Day 15) | ± 3 days |
| Visits 17-41 (Clinic; OLE Study Days 30, 60, 90, 180, 270, 360, 450, 540*, 630, 720*, 810, 900*, 990, 1080*, 1170, 1260*, 1350, 1440*, 1530, 1620*, 1710, 1800*, 1890, 1980*, 2070) | ± 4 days |

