6.2.6 Clinic Visit 42: End of Study/Early Termination

The End-of-Study participation in Part 2 for an individual subject occurs after he/she has received IMP for up to 5 years in the Part 2 OLE Treatment Period, or until ZX008 is approved in a subject's country of residence and listed on a patient's health plan formulary, whichever occurs first. The End-of-Study visit may also occur if the subject withdraws participation from in Part 2 or the Sponsor terminates the study.

Subjects will visit the clinic for the End-of-Study visit if one the following events occur:

1. The subject withdraws or is withdrawn from participation in the study.
2. The Sponsor terminates the study.
3. The subject completes all study related visits and procedures (at least up to Month 12, but extensions may be granted for up to 72 months).
4. ZX008 is approved in a subject's country of residence and is listed on a patient's health plan formulary

The following procedures will be performed for subjects who did not extend Part 2 participation past 12 months:

- Review current seizure activity (number/type/duration) from diary since previous visit
- Record concomitant medications

ZX008 (Fenfluramine Hydrochloride)

ZX008-1601 Clinical Study PA 4.0 (Japan) 25 July 2022

- Complete physical examination, including height and weight, and calculation of BMI
- Complete neurological examination
- Obtain vital signs
- 12-lead ECG
- Doppler ECHO (must be performed within 3 weeks of the visit; if subject terminates early from the study, the ECHO should be scheduled as soon as practical). If the previous ECHO was completed ≤ 30 days prior to early termination, the Visit 30 ECHO will not be performed provided the parent/guardian agrees to bring the subject to the clinic for the cardiac follow-up visit (see Table 12).
- Urine or serum pregnancy test for females of child-bearing potential
- Laboratory evaluation (serum chemistry, hematology, immunoglobulin, hormones, and urinalysis) (urine for urinalysis may be collected at home, the night before the clinic visit, as long as collection procedures are followed to maintain sample stability)
- Urine or serum THC panel
- Whole blood CBD
- Collect plasma sample for AED PK evaluation (must document time of last dose)
- Tanner Staging for subjects > 7 to 18 years of age ([Appendix 5](#))
- Collect and review diary C-SSRS Since Last Visit Assessment ([Appendix 2](#))
- CGI-I (assessed by parent/caregiver)
- CGI-I (assessed by investigator)

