6.4 ESTIMATED BLOOD VOLUME COLLECTION

The maximum total blood volume collected during Part 1 of the study for clinical laboratory testing, genotyping, and PK will be approximately 84.0 mL, as outlined in [Table 13](#) The

ZX008 (Fenfluramine Hydrochloride)
ZX008-1601 Clinical Study PA 4.0 (Japan) 25 July 2022

maximum total blood volume collected during Part 2 of the study for clinical laboratory testing and PK will be variable as the clinical laboratory testing will be performed as clinically indicated for the majority of in clinic visits after Visit26/Month 24, and will be approximately 104.0 mL at the minimum and will equal up to 351.5 mL , as outlined in [Table 14](#).

Table 13: Maximum Estimated Blood Volume Collection for Part 1*

| PART 1 | Visit 1 (Day -28) | Visit 3 (Day -1) | Visit 8 (Day 43) | Visit 12 (Day 99) | TOTAL |
|--|--------------------------|--------------------------|--------------------------|--------------------------|----------------|
| Coagulation | | 3.0 mL | | | 3.0 mL |
| Chemistry | 5.0 mL | 5.0 mL | 5.0 mL | 5.0 mL | 20.0 mL |
| Pregnancy test (serum) | included in Chemistry | included in Chemistry | included in Chemistry | included in Chemistry | 0.0 mL |
| Hormones | | 5.0 mL | 5.0 mL | 5.0 mL | 15.0 mL |
| Immunoglobulin | 2.5 mL | 2.5 mL | 2.5 mL | 2.5 mL | 10.0 mL |
| Hematology | 2.0 mL | 2.0 mL | 2.0 mL | 2.0 mL | 8.0 mL |
| Genotype Panel | | 4.0 mL | | | 4.0 mL |
| AED PK plasma sample* | | 2.0 mL | 2.0 mL | 2.0 mL | 6.0 mL |
| ZX008 PK plasma sample | | | 8.0 mL | | 8.0 mL |
| Volume for flushing indwelling catheter | | | 2.0 | | 2.0 mL |
| Cannabidiol/THC | 2.0 mL | 2.0 mL | 2.0 mL | 2.0 mL | 8.0 mL |
| TOTAL | 11.5 mL | 25.5 mL | 28.5 mL | 18.5 mL | 84.0 mL |

AED=Anti-epileptic drugs; PK=pharmacokinetics

*Blood collection for AED pharmacokinetic evaluation may be collected on Visits 6 and 10 if clinically indicated. If collected during these visits, the total blood volume per subject would equal up to 88.0 mL.

Table 14. Maximum Estimated Blood Volume Collection for Part 2*

| PART 2 | Visit 19 (Day 90) | Visit 20 (Day 180) | Visit 21 (Day 270) | Visit 22 (Day 360) | Visits 23- 42 (in clinic only) | TOTAL |
|-------------------------------|--------------------------|--------------------------|--------------------------|--------------------------|---|-----------------|
| Chemistry | 5.0 mL | 5.0 mL | 5.0 mL | 5.0 mL | | 20.0 mL |

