| Pregnancy test (serum) | included in Chemistry | included in Chemistry | included in Chemistry | included in Chemistry | 2.5 mL | 2.5 mL |
| Hormones | 5.0 mL | 5.0 mL | 5.0 mL | 5.0 mL | | 20.0 mL |
| Immunoglobulin | 2.5 mL | 2.5 mL | 2.5 mL | 2.5 mL | | 10.0 mL |
| Hematology | 2.0 mL | 2.0 mL | 2.0 mL | 2.0 mL | | 8.0 mL |
| AED PK plasma sample | 2.0 mL | 2.0 mL | 2.0 mL | 2.0 mL | | 8.0 mL |
| Cannabidiol/THC | 2.0 mL | 2.0 mL | 2.0 mL | 2.0 mL | | 8.0 mL |
| TOTAL | 18.5 mL | 18.5 mL | 18.5 mL | 18.5 mL | 30 mL | 104.0 mL |

AED=Anti-epileptic drugs; PK=pharmacokinetics

*Laboratory testing may be conducted on Visits 16-18 and 23-42 if clinically indicated. After Visit 26, in-clinic visits will occur every 6 months. If collected during these visits, the total blood volume per subject would equal up to 351.5mL.

*In concordance with The Seattle Children's Research Foundation Guidance ([Appendix 9](#)),

ZX008 (Fenfluramine Hydrochloride)
ZX008-1601 Clinical Study PA 4.0 (Japan) 25 July 2022

blood collection volumes for children weighing up to 15 kg will be:

- The maximum allowable volume of blood in one draw is 22-30 mL (2.5% of total blood volume)
- The maximum in a 30-day period is 44-60 mL.

On Part 1 Day 43/Visit 8 the pharmacokinetic blood draw will be completed as the priority and the blood draw for chemistry and hematology will be skipped for those subjects who weigh less than 13.5 kg, unless medical concerns (for example, from previous tests or reported side effects) prioritize chemistry and/or hematology.

If blood collection is restricted due to volume or due to inability to draw adequate volume, collection should be prioritized as shown in [Table 15](#)

Table 15: Priorities for Blood Sample Collections

| Assessment | Priority |
|---|---|
| ZX008 PK sample | Priority 1 |
| Clinical chemistry | Priority 2 |
| Cannabidiol | Priority 2 |
| AED plasma sample | Priority 2 |
| LH, FSH, estradiol, testosterone, GH, prolactin | Priority 3 |
| Hematology | Priority 3 |
| IGF-1 | Priority 4 |
| Genotyping | One time optional collection any time during or after Visit 3 (Randomization) in Part 1 |
| Coagulation | One time collection any time before Part 1 PK day |

ZX008 (Fenfluramine Hydrochloride)
ZX008-1601 Clinical Study PA 4.0 (Japan) 25 July 2022

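### Section 6.2.4 leaves hormones and immunoglobulin out of the Month 12 laboratory list, but Table 14 budgets both at that visit

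*Protocol*

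**What the plan says.** Section 6.2.4 gives the Visit 22 laboratory work as "Laboratory evaluation (serum chemistry and hematology, and urinalysis". Hormones and immunoglobulin do not appear anywhere in that visit's list.

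Table 14 (Section 6.4) has a Visit 22 (Day 360) column. Its hormone row for Visits 19 to 22 reads "Hormones | 5.0 mL | 5.0 mL | 5.0 mL | 5.0 mL", and its immunoglobulin row has 2.5 mL at each of the same four visits. Section 6.4 says the Part 2 volume "will be approximately 104.0 mL at the minimum and will equal up to 351.5 mL". The Table 14 footnote on testing only when clinically indicated covers Visits 16-18 and 23-42, so Visit 22 is outside it.

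The neighbouring lists name both panels:

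- Section 6.2.3 (Visits 17-21) has "Laboratory evaluation (serum chemistry, hematology, immunoglobulin, hormones, and urinalysis; at Months 3, 6 and 9 unless otherwise clinically indicated".
- Section 6.2.6, for subjects who do not extend past Month 12, has "Laboratory evaluation (serum chemistry, hematology, immunoglobulin, hormones, and urinalysis".

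After Month 12, Section 6.2.5 puts laboratory evaluation under the heading "Only if clinically indicated". Section 6.2.6 does the same at end of study for subjects who extended.

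Section 6.2 states that Part 2 procedures "will be conducted according to the Schedule of Assessments in Table 2". Table 2 marks a laboratory evaluation at Visit 22, but its row label ends in *etc* and does not define the panel.

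**The concern.** Two current parts of the protocol give different blood draws for the same visit, and the governing schedule does not choose between them. A site working from the visit description would omit two panels that the blood-volume plan treats as scheduled.

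Visit 22 is also the last visit at which these panels could be scheduled for a subject who continues, because later testing depends on clinical indication. The hormone group in Section 7.2.6 covers prolactin, thyroid function, growth and puberty markers. Table 16 makes prolactin at or above twice the upper limit of normal an adverse event of special interest. No scheduled test would then find an asymptomatic rise at Month 12. Laboratory parameters belong to the Part 2 primary safety objective (Section 2.2.1), and Section 10.1 sets a Part 2 interim analysis once all Cohort B subjects complete 12 months, so the content of the Month 12 panel matters for that report.

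**Working it through.** **Inputs (Table 14, Visit 22 column).** Chemistry 5.0, hormones 5.0, immunoglobulin 2.5, hematology 2.0, AED PK 2.0, cannabidiol/THC 2.0 mL. Visits 19, 20 and 21 have the same entries. The pregnancy-test row gives 2.5 mL under Visits 23-42, in-clinic only.

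**Visit 22 total.** 5.0 + 5.0 + 2.5 + 2.0 + 2.0 + 2.0 = 18.5 mL, as printed. Without hormones and immunoglobulin: 18.5 − 7.5 = 11.0 mL. The 7.5 mL is about 41% of the visit's draw (7.5 / 18.5).

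**Part 2 minimum.** The schedule implies 12 in-clinic visits after Visit 22: Visits 23, 24, 25 and 26, then every second visit from 28 to 42 (eight visits). Pregnancy tests: 12 × 2.5 = 30 mL, the printed column total. Minimum: 4 × 18.5 + 30 = 74 + 30 = 104.0 mL, as printed. Without the two panels at Visit 22: 104.0 − 7.5 = 96.5 mL.

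**Part 2 maximum.** The optional laboratory visits are 16, 17 and 18 plus those 12, so 15. The panel without cannabidiol/THC is 18.5 − 2.0 = 16.5 mL. Maximum: 104.0 + 15 × 16.5 = 104.0 + 247.5 = 351.5 mL, as printed. Without the two panels at Visit 22: 351.5 − 7.5 = 344.0 mL.

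| Quantity | Printed | With both panels | Section 6.2.4 as written |
|---|---|---|---|
| Visit 22 | 18.5 mL | 18.5 mL | 11.0 mL |
| Part 2 minimum | 104.0 mL | 104.0 mL | 96.5 mL |
| Part 2 maximum | 351.5 mL | 351.5 mL | 344.0 mL |

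**Other visits.** Seven other visits have their own column in Tables 13 and 14: Visits 1, 3, 8, 12, 19, 20 and 21. Each agrees with its section's list on hormones and immunoglobulin. Only Visit 22 does not.

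**Does the schedule table settle it?** The equivalent row in Table 1 is marked at Visit 1, where Section 6.1.1.1 lists "Laboratory evaluation (serum chemistry, hematology, immunoglobulin, and urinalysis" and Table 13 budgets no hormones. A mark in that row therefore does not by itself mean the full panel.

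**The case against.** Section 7.2.6 lists the hormones and immunoglobulins and says they are assessed as described in the schedule tables, and Table 2 marks Visit 22. Read together, these lean towards the full panel at Month 12. That supports the correction, but the screening visit shows the reading is not conclusive.

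Table 14 is titled a maximum estimate, so drawing less breaches no limit. The 104.0 mL called a minimum includes 30 mL of serum pregnancy tests, which apply only to females of child-bearing potential and may be done on urine. The table's printed row totals also add to 76.5 mL rather than 104.0 mL, because the pregnancy row is totalled as 2.5 mL, and the count of 12 in-clinic visits is inferred. All of this is fair: Table 14 does not prove that each draw is mandatory. It does show that whoever computed the volumes counted both panels at Visit 22.

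The safety consequence is limited. Hormones are also scheduled at Part 1 Visits 3, 8 and 12 and at open-label Months 3, 6 and 9. Tanner staging remains at Visit 22, events of special interest are still recorded, and hormones rank only third (IGF-1 fourth) in the blood-collection priorities. Section 2.3.2 names only hematology, chemistry and urinalysis as laboratory endpoints. No efficacy test or dosing rule uses a Month 12 hormone or immunoglobulin value.

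The transition table in Table 2 lists last visits only from Month 24 to Month 36, so the remaining subjects may all be past Visit 22. For them, new text changes no blood draw. This limits the practical effect but does not remove the contradiction.

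**Conclusion.** The contradiction is real and is in current text. Section 6.2.4 is the outlier against Table 14, both Section 6.4 totals, and the lists in Sections 6.2.3 and 6.2.6. It looks like a drafting slip; nothing indicates that the tests were deliberately dropped.

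The size is 7.5 mL at one visit and, if Section 6.2.4 is followed, three instead of four scheduled Part 2 hormone and immunoglobulin time points. The last scheduled test for continuing subjects moves from Month 12 to Month 9. Whether any data were missed depends on which text sites followed, and the protocol cannot show that. Reproducing the two Part 2 totals rests on the inferred count of 12 in-clinic visits; the Visit 22 total of 18.5 mL does not. The point is of modest importance: it concerns safety monitoring and has no bearing on efficacy.

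**What to change.** Replace the Section 6.2.4 laboratory line with the panel already used in Section 6.2.6, "Laboratory evaluation (serum chemistry, hematology, immunoglobulin, hormones, and urinalysis", so that it agrees with Table 14. For subjects who have already passed Month 12, document which panel was drawn at Visit 22, so that the Month 12 safety summaries can state how many subjects contributed hormone and immunoglobulin results.

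The cost is one line of text and a check of existing laboratory records. No extra blood volume is needed, since Table 14 already includes it.
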